### **Treatment Related Adverse Events**

Treatment Related Adverse Events are treatment emergent adverse events with cause categorized by the investigator as related to study treatment. Events that are continuations of baseline abnormalities (signs and symptoms) are not considered treatment emergent, and hence are not considered treatment related, unless there is an increase in grade over baseline.

#### **7.2.5. ECG and QTc Interval**

ECG data will be collected. See Schedule of Activities in the protocol for details. 12 lead ECGs will be summarized. The baseline evaluation for ECGs is the pre-dose value on Cycle 1/Day 1. If the pre-dose value is not collected, the ECG closest but prior to Cycle 1/Day 1 will be used. If the closest ECGs are triplicate ECGs (or only 2), they will be averaged. If the closest ECG is a single, that will be used as baseline.

*QT intervals will be corrected for heart rate (QTc) using Fridericia's correction factors (QTcF). The adequacy of the correction method will be assessed graphically (plots of QT and QTcF versus RR) and supplementary transformations may be considered, as appropriate. Data will be summarized and listed for QT, HR, RR, PR, QRS and QTcF by treatment and dose. Descriptive statistics (n, mean, median, standard deviation, minimum, and maximum) will be used to summarize the absolute QTcF value and changes from baseline in QTcF after treatment by compound, dose and by time point. For each patient and by treatment, the maximum change from baseline will be calculated as well as the maximum post-baseline value across time-points. Outlier analysis of the QTcF data will be conducted and summarized as follows:*

- *The number of patients with maximum change from baseline in QTcF (<30, 30-60, and ≥60 ms).*
- *The number of patients with maximum post-dose (post-baseline) QTcF (<450, 450-<480, and >=480 ms).*

*In addition, the number of patients with corrected and uncorrected QT values ≥500 msec will be summarized.*

*Shift tables will be provided for baseline vs. worst on study QTcF using Maximum CTCAE Grade. As well as tables of ECG abnormality at baseline (yes, no, not done: (n, %)). Patients experiencing clinically-relevant morphological ECG changes will be summarized (including frequency and percentage).*

*If more than one ECG is collected at a nominal time post dose (for example, triplicate ECGs), the mean of the replicate measurements will be used to represent a single observation at that time point. If any of the three individual ECG tracings has a QTc value  $\geq 500$  msec, but the mean of the triplicates is not  $\geq 500$  msec, the data from the subject's individual tracing will be described in a safety section of the study report in order to place the  $\geq 500$  msec value in appropriate clinical context. However, values from individual tracings within triplicate measurements that are  $\geq 500$  msec will not be included in the categorical analysis unless the average from those triplicate measurements is also  $\geq 500$  msec. Changes from baseline will be defined as the change between QTcF post dose and the pre-dose values on Day 1.*

*The effect of drug concentrations on QTcF change from baseline will be explored graphically. Additional concentration-QTcF analyses may be performed. Data may be pooled with other study results and/or explored further with PK/PD models.*

#### **7.2.6. Immunogenicity**

Anti-PF-06650808 antibody data will be collected at baseline and post-randomization according to the protocol.

### **7.3. PK Endpoints**

Blood samples for PK analysis of PF-06650808 (ADC), PF-06460005 (total antibody), and PF-06380101 (unconjugated payload) will be taken according to the Schedule of Activities given in the protocol.

- **Pharmacokinetic parameters of PF-06650808 (ADC):**

Cycle 1 -  $C_{max}$ ,  $T_{max}$ ,  $AUC_{last}$ ,  $AUC_{inf}$ ,  $AUC_{\tau}$ ,  $t_{1/2}$ ,  $CL$ , and  $V_{ss}$  as data permit.

Cycle 4 -  $C_{max}$ ,  $T_{max}$ ,  $AUC_{last}$ ,  $AUC_{\tau}$ ,  $t_{1/2}$ , and  $R_{ac}$  as data permit.

- **Pharmacokinetic parameters of PF-06460005 (total antibody) and PF-06380101 (unconjugated payload):**

Cycle 1 -  $C_{max}$ ,  $T_{max}$ ,  $AUC_{last}$ ,  $AUC_{inf}$ ,  $AUC_{\tau}$ , and  $t_{1/2}$  as data permit.

Cycle 4 -  $C_{max}$ ,  $T_{max}$ ,  $AUC_{last}$ ,  $AUC_{\tau}$ ,  $t_{1/2}$ , and  $R_{ac}$  as data permit.

PK parameters will be derived from the concentration-time data as follows:

Parameter	Definition	Method of Determination
$AUC_{last}$	Area under the concentration-time profile from time zero to the time of the last quantifiable concentration	Linear/Log trapezoidal method
$AUC_{\tau}$	Area under the concentration-time profile from time zero to the time $\tau$ , the dosing interval	Linear/Log trapezoidal method
$AUC_{inf}$	Area under the concentration-time profile from time zero extrapolated to infinite time	$AUC_{(0-t[last])} + (C_{last}^* / kel)$ , where $C_{last}^*$ is the predicted serum concentration at the last quantifiable time point estimated from the log-linear regression analysis.
$C_{max}$	Maximum observed concentration	Observed directly from data
$T_{max}$	Time for $C_{max}$	Observed directly from data as time of first occurrence
$T_{1/2}$	Terminal elimination half-life	$\log(2) / kel$ , where $kel$ is the terminal phase rate constant calculated by a linear regression of the log-linear concentration-time curve. Only those data points judged to describe the terminal log-linear decline will be used in the regression.
CL	Clearance	$Dose / AUC_{inf}$ for cycle 1; $Dose / AUC_{\tau}$ for cycle 4
$V_{ss}$	Volume of distribution at steady state	$CL \times MRT$
$R_{ac}$	Observed accumulation ratio	$AUC_{cycle\ 4,\ \tau} / AUC_{cycle\ 1,\ \tau}$

CCI

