3.2. Dose Escalation Phase (Part 1)

A modified continual reassessment method (mCRM) targeting a DLT rate of 25% will be utilized for Part 1 (dose escalation phase) (Goodman et al, 1995; O'Quigley et al, 1990).^{7,14} Patients will be enrolled in cohorts of 2 to 4, starting with 0.2 mg/kg for the first cohort. The possible doses explored will be from a fine grid of doses ranging from 0.2 mg/kg to 6.4 mg/kg. If a high DLT rate is observed at the starting dose of 0.2 mg/kg, a lower dose such as 0.14 mg/kg (a 30% reduction from starting dose) or lower will be considered. The study may be stopped if the drug is deemed not tolerable at the lowest reduced dose. The mCRM model will determine the next dose level based on the DLT rate using a 30%, 69% and 100% dose increment for 0, 1 or 2 dose skips respectively.

Starting with the second cohort, patients will be assigned to a dose that is closest to the current MTD prediction based on a model that mCRM utilized to learn about overall dose-toxicity relationship. This model is updated after DLT assessment of each cohort. At any given point in this phase, doses can be escalated, deescalated, unchanged or revisited, but always aiming towards the target MTD. To prevent overly aggressive dose-escalation, the maximum allowed dose increase will be limited to 2 increments at a time (ie, no more than 100% dose increase at a time). In addition, if two clinically significant Grade 2 toxicities of the same type are seen in a cohort, dose escalation will be limited to no greater than 69% for the next cohort. If there is one additional case of the same Grade 2 toxicity or two other cases of clinically significant Grade 2 toxicities of the same type, dose escalation will again be limited to no greater than 69% for the next cohort; otherwise dose escalation following the mCRM algorithm will resume. Grade 2 toxicities will not be considered clinically significant if a corresponding Grade 3 toxicity exists (by NCI CTCAE v 4.03); Grade 2 toxicities without a corresponding Grade 3 toxicity will be considered clinically significant (eg, Grade 2 alopecia, dry skin, libido decrease). In addition, Grade 2 nausea, vomiting, and diarrhea will not be considered clinically significant unless it has been optimally medically managed.

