5.2.6. Dose Reductions

Dose reductions or delays in the administration of PF-06650808 are permitted as described below for PF-06650808 related toxicity. The sponsor should be notified when dose reductions are planned and consulted for any dose reduction related questions.

Once a dose has been reduced for a given patient, all subsequent cycles should be administered at that dose level, unless further dose reduction is required. The reduced dose will be considered the maximum dose for all subsequent cycles for that patient. Doses should be reduced to the next lowest cohort dose level. Dose re-escalation is not allowed.

Patients enrolled in the first cohort should be discontinued from the study if more than 1 dose reduction is required. Patients enrolled in subsequent cohorts should be discontinued from the study if more than 2 dose reductions are required. For patients experiencing an adverse

event related to PF-06650808 that fails to recover to CTCAE Grade 1 (or within 1 grade of starting values for pre-existing laboratory abnormalities) leading to treatment delay of >2 weeks should be discontinued unless discussed with the sponsor.

The following table summarizes the actions following the toxicities observed during the study period.

Event	Action
Grade 3 or 4 nonhematologic toxicity considered at least possibly related to PF-06650808 per investigator judgment (including persistent nausea, vomiting, diarrhea despite optimal medical therapy)	
 Hold PF-06650808 infusion until recovery to Grade 0-1 or baseline and reduce by 1 dose level. Discontinue PF-06650808 if dose delay is more than 2 weeks. If toxicity reoccurs despite reduction, patient may be dose reduced again by another dose level upon recovery to grade 0-1 or baseline unless the patient is in the first dose group, then only 1 dose reduction is allowed. Prompt palliative measures are strongly encouraged (eg, anti-emetics). Patients who experience Grade 4 non hematologic toxicities despite intervention should be discontinued from the study.

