9.5.1. Analysis of Pharmacokinetics

Drug concentrations of ADC (PF-06650808), total antibody (PF-06460005) and unconjugated payload (PF-06380101) will be measured using validated methods. PK parameters will be determined from the respective concentration-time data using standard noncompartmental methods. Actual sample collection times will be used for the parameter calculations. For ADC (PF-06650808) and total antibody (PF-06460005), PK parameters including maximum concentration (C_{max}), time to maximum concentration (T_{max}), area under the concentration-time curve (AUC_{inf} and AUC_{τ}), clearance (CL), volume of distribution (V_{ss}), terminal elimination half-life ($t_{1/2}$), and accumulation ratio (R_{ac}) will be calculated. For unconjugated payload (PF-06380101), PK parameters including maximum concentration (C_{max}), time to maximum concentration (T_{max}), area under the concentration-time curve (AUC_{inf} and AUC_{τ}), terminal elimination half-life ($t_{1/2}$), and accumulation ratio (R_{ac}) will be calculated.

Drug concentrations of ADC (PF-06650808), total antibody (PF-06460005) and unconjugated payload (PF-06380101) will be summarized graphically and with descriptive statistics by dose, cycle, and the nominal PK sampling time. Noncompartmental PK parameters will be summarized descriptively by dose and cycle.

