### 9.2.2.2. Pharmacokinetics Analyses

#### Pharmacokinetic Parameters

To assess the pharmacokinetics of PF-06650808 (ADC), PF-06460005 (total antibody) and PF-06380101 (unconjugated payload), the PK parameters detailed in [Section 7.3](#) will be listed and summarized for subjects in the PK analysis set (as defined in [Section 6.4](#)). Missing values will be handled as detailed in [Section 8](#). Each PK parameter will be summarized by dose and cycle and will include the set of summary statistics as specified in the table below:

Parameter	Summary statistics
AUC last , AUC inf , AUC τ , C max , CL, V ss , and R ac	N, arithmetic mean, median, cv%, standard deviation, minimum, maximum, geometric mean
t 1/2	N, arithmetic mean, median, cv%, standard deviation, minimum, maximum
T max	N, median, minimum, maximum

There will be 1 summary table presenting all PK parameters. This will include data from all cohorts and will be summarized by dose group and cycle.

To assess the relationship between the PK parameters and dose, dose normalized AUCinf, AUClast, AUCτ, and Cmax will be plotted against dose (using a logarithmic scale), and will include individual subject values and the geometric means for each dose. Geometric means will have a different symbol than the individual values. The values will be dose normalized (to a 1 mg/kg dose) by dividing the individual values and raw geometric means by dose. A footnote will be added to the plots to indicate that geometric means are presented are presented on the plot.

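### R_ac divides Cycle 4 AUCτ by Cycle 1 AUCτ with no dose term, so it reads low in patients whose dose was reduced at or before Cycle 4

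*SAP*

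**What the plan says.** The parameter table in SAP 7.3 gives R_ac, the "Observed accumulation ratio", as AUCτ in Cycle 4 divided by AUCτ in Cycle 1. It is planned for the ADC, the total antibody and the unconjugated payload. Dose does not enter the formula, although the same table uses dose to derive clearance.

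Protocol 5.2.6 allows the dose to change between those cycles:
- On step size: "Doses should be reduced to the next lowest cohort dose level".
- On permanence (the quote stops one word short of the sentence's end): "Once a dose has been reduced for a given patient, all subsequent cycles should be administered at that dose level, unless further dose reduction is". Re-escalation is not allowed.
- On number: "Patients enrolled in subsequent cohorts should be discontinued from the study if more than 2 dose reductions are required". In the first cohort only one reduction is allowed.

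The gap between dose levels follows from Protocol 3.2, where the next dose is set "using a 30%, 69% and 100% dose increment for 0, 1 or 2 dose skips respectively". Below the starting dose, "a lower dose such as 0.14 mg/kg (a 30% reduction from starting dose) or lower will be considered".

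On reporting, Protocol 9.5.1 says: "Noncompartmental PK parameters will be summarized descriptively by dose and cycle". SAP 9.2.2.2 does the same and gives no rule for a patient whose Cycle 4 dose differs from the Cycle 1 dose. That section does normalise by dose, but only for the plots of AUC and C_max against dose: "The values will be dose normalized (to a 1 mg/kg dose) by dividing the individual values and raw geometric means by dose". R_ac is not among the parameters plotted.

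**The concern.** An accumulation ratio is meant to compare exposure at a later cycle with exposure at the first cycle under the same dosing. If the dose has fallen in between, the numerator falls with it, and the ratio no longer isolates accumulation.

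Multiple-dose PK is a secondary objective in both parts, and Protocol 3.1 allows doses, schedule and PK timepoints to be reconsidered on emerging safety and PK data. The affected group can be foreseen. The design targets a 25% DLT rate, and patients with a DLT may continue with a modified dose. At a true rate of 25%, about 0.25 × 20 = 5 of the 20 Part 2 patients would have a Cycle 1 DLT. The documents do not say how many would continue at a lower dose and reach Cycle 4.

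**Working it through.** **Inputs from the documents.** The dosing interval τ is 21 days (Protocol 5.2.3). Adjacent grid doses differ by 1.3-fold, and cohorts may be 1.69-fold or 2-fold apart after skips (Protocol 3.2). Two of the plan's own figures reproduce: 1.3² − 1 = 69%, and 0.2 × 0.7 = 0.14 mg/kg. One step down therefore multiplies the dose by r = 1/1.3 = 0.769, 1/1.69 = 0.592 or 1/2 = 0.50, and from 0.2 to 0.14 mg/kg by r = 0.70. A step down of one grid position is a 23% cut, not 30%, because the 30% is measured upward.

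**Assumptions.** Linear one-compartment PK with the short infusion treated as instantaneous, and a half-life of 2 to 14 days. The documents state no half-life; it is used only to size carry-over from earlier doses.

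**Formula.** Let q = 2^(−21/half-life), the fraction carried from one cycle to the next, and let D1 to D4 be the doses in Cycles 1 to 4. Then

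R_ac (SAP formula) = (D4 + D3·q + D2·q² + D1·q³) / D1.

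With constant dose this is 1 + q + q² + q³.

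**Worked case, half-life 7 days.** q = 2^(−3) = 0.125.
- Constant dose: 1 + 0.125 + 0.0156 + 0.0020 = 1.143.
- One 1.3-fold step down from Cycle 2: 0.769 × 1.1406 + 0.0020 = 0.879, which is 23% low.
- The same step first taken at Cycle 4: 0.769 + 0.1426 = 0.912, which is 20% low.
- One 2-fold step down from Cycle 2: 0.50 × 1.1406 + 0.0020 = 0.572, which is 50% low.

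**Change in R_ac relative to constant dose, one step down:**

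| Step (r) | 2 days, from Cycle 2 or 4 | 7 days, from Cycle 2 | 7 days, from Cycle 4 | 14 days, from Cycle 2 | 14 days, from Cycle 4 |
|---|---|---|---|---|---|
| 1.3-fold (0.769) | −23% | −23% | −20% | −22% | −15% |
| 0.2 to 0.14 mg/kg (0.70) | −30% | −30% | −26% | −29% | −20% |
| 1.69-fold (0.592) | −41% | −41% | −36% | −40% | −27% |
| 2-fold (0.50) | −50% | −50% | −44% | −49% | −33% |

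With no carry-over the understatement is 1 − r, which gives the limits of 23%, 41% and 50%. Two 2-fold steps (r = 0.25, both treated as made at the same cycle) give −49% to −75%. A first reduction at Cycle 5 or later gives 0%, since D1 to D4 are equal.

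**Group level, if nobody is excluded.** At the no-carry-over limit, with m of n patients reduced, the geometric mean is multiplied by r^(m/n). With 1 of 6 reduced this is 0.96 (1.3-fold) to 0.89 (2-fold). With 2 of 6 it is 0.92 to 0.79.

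**Does dividing each AUCτ by its own dose repair it?** The normalised ratio is the expression above times D1/D4. For one step down:
- Reduction from Cycle 2 or 3: within about 2% of the constant-dose value for half-lives up to 7 days, and +1% to +11% at 14 days.
- Reduction first made at Cycle 4: +0% to +3% at 2 to 4 days, +4% to +12% at 7 days, +10% to +34% at 14 days. Carry-over from the earlier, higher doses is then divided by the lower dose.

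**The case against.** The strongest reply is SAP 8.3. A PK estimate known to be biased is footnoted and left out of summaries, and a recorded dose reduction makes this bias known. That is a fair reading, and it could keep the affected values out. But the rule does not name dose reduction. Its example is an unexpected event, vomiting before absorption is complete, whereas a reduction under Protocol 5.2.6 is planned management. Two analysts could apply the rule differently and produce different R_ac tables from the same data.

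Second, a reader might infer that accumulation would go unseen. The documents do not support that. SAP 9.2.2.2 plots predose concentrations by cycle with individual profiles and summarises AUCτ by dose and cycle. SAP 9.2.4 lists administered dose and any reduction for each patient and cycle. The information is there, but it is not linked to R_ac.

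Third, it is tempting to say the bias is worst at the MTD because reductions cluster there. This is plausible, but neither document states it or gives a frequency.

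Fourth, dose normalisation might seem to settle the matter. It assumes linear PK, which the dose-normalised plots have yet to examine, and it overcorrects for a reduction at Cycle 4 when carry-over is material. This objection stands and shapes the fix.

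**Conclusion.** The point holds in a bounded form. The SAP formula is sound for patients on a constant dose. It is too low for those reduced at or before Cycle 4 who have evaluable AUCτ in Cycles 1 and 4. For one such patient and one step down, the shortfall is about 15–23%, 27–41% or 33–50% for 1.3-, 1.69- and 2-fold spacing. The direction is the same in every case run. The sizes rest on linear PK and the assumed half-life range.

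A reader might infer that every dose-reduced patient is affected. The documents do not support this: reductions from Cycle 5 onward do not enter the ratio, and a patient without Cycle 4 PK has no R_ac. Nor are 23%, 41% and 50% fixed values; they are the limits without carry-over.

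The consequence is modest. R_ac is a descriptive secondary PK parameter, the study tests no hypothesis, and no escalation, stopping or MTD rule uses it.

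**What to change.** In SAP 7.3 and 9.2.2.2, summarise R_ac in patients who received the same dose in Cycles 1 to 4. Equivalently, name a dose reduction at or before Cycle 4 in the SAP 8.3 rule as a reason to footnote and exclude R_ac.

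As a companion, report (AUCτ Cycle 4 / dose Cycle 4) / (AUCτ Cycle 1 / dose Cycle 1) using actual doses. Flag the dose-reduced patients and the cycle of reduction, and note that the ratio assumes linear PK and reads high when the reduction falls at Cycle 4 and carry-over is material.

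The cost is one formula and a sentence or two. No new data are needed, because dose per cycle is already listed. The downside is fewer patients in the main R_ac summary, which matters in cohorts of 2 to 4. SAP 8.3 also withholds statistics when more than half of a group's values are not calculated, so the SAP should say whether these exclusions count toward that limit.

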## 7.5. Covariates

Not applicable.

## 8. HANDLING OF MISSING VALUES

### 8.1. Missing Dates

In compliance with Pfizer standards, if the day of the month is missing for any date used in a calculation, the 1st of the month will be used to replace the missing date unless the calculation results in a negative time duration (eg, date of onset cannot be prior to day one date). In this case, the date resulting in 0 time duration will be used. Pfizer standards are also used if both month and day are missing (Jan 1 unless negative time duration). This excludes the pharmacokinetic, ECG, and pharmacodynamic analyses, which will only use the actual date collected or if date not available deem the data missing.

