- **Progression Free Survival (PFS)** - is defined as the time from Cycle 1 Day 1 (C1D1) to first documentation of disease progression or to death due to any cause, whichever occurs first. Subjects last known to be 1) alive 2) on treatment or within the post-treatment follow-up period and 3) progression-free, are censored at the date of the last disease assessment that verified lack of disease progression. Subjects who start new anti-cancer treatment prior to the end of post-treatment follow-up period and have adequate baseline and on-treatment objective disease assessments without evidence of progressive disease are censored at the date of the last objective disease assessment. Subjects with inadequate baseline or no on-study disease assessments are censored at C1D1 unless death occurred prior to the first planned assessment (in which case the death is an event). Subjects with at least one on-study disease assessment who discontinue treatment without disease progression and without death within 28 days of discontinuation are censored at the date of the last objective disease assessment that verified lack of disease progression (if progression or death is within 28 days of discontinuation the progression or death is an event). Subjects with documentation of progression or death after an unacceptably long interval ( $>16$  weeks) since the previous disease assessment will be censored at the time of the previous assessment.

PFS (days) = [progression/death date – C1D1 + 1].

- **Overall survival (OS)** is defined as the time from initial dose until death from any cause, and is measured in the intent-to-treat population.

More details of censoring are provided in [Appendix 3](#).

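### SAP 8.1 can date a death before the patient was last documented alive, and sets OS to zero when only the year of first dose is known

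*SAP*

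**What the plan says.** SAP section 8.1 applies "if the day of the month is missing for any date used in a calculation". The 1st "of the month will be used to replace the missing date unless the calculation results in a negative time duration", and the illustration given is that "date of onset cannot be prior to day one date". When the limit is reached, "In this case, the date resulting in 0 time duration will be used". If the month is missing too, 1 January is used, subject to the same limit. The exemption is narrow: "This excludes the pharmacokinetic, ECG, and pharmacodynamic analyses". Time-to-event analyses are therefore covered.

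SAP section 7.1 says that OS "is defined as the time from initial dose until death from any cause". PFS in the same section is the event date minus Cycle 1 Day 1, plus 1. SAP section 8.2 refers only to Appendix 3, where Tables 3 and 4 list censoring situations for PFS, duration of response and time to progression. Neither the endpoint definitions nor those tables contain a rule for a partly known death date, or a floor at the last date known alive.

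**The concern.** An earliest-date convention is reasonable for adverse event onset, where first dose is the natural lower bound. A death has a tighter one: the patient cannot have died before a visit that he or she attended. Because OS and PFS both start at first dose, a check for negative duration acts only at first dose and ignores every later contact.

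Two results follow. A death with the day missing can be dated before a visit, laboratory sample or scan already in the database. A death known only to the year of first dose is moved to the day of first dose, however long the patient was followed. Both make recorded survival too short, and the first creates records that contradict each other.

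**Working it through.** The documents give no figure to reproduce here. The rule was applied as written.

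**Rule as a formula**
- Day missing: imputed date = later of (1st of known month, first dose).
- Month and day missing: imputed date = later of (1 January of known year, first dose).
- OS = imputed date − first dose. PFS = the same + 1.

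**Worked cases** (dates assumed; first dose 10 March 2015)

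| True death | Last seen alive | Missing | Imputed | OS by rule | True OS |
|---|---|---|---|---|---|
| 25 Jun 2015 | 16 Jun 2015 | day | 1 Jun 2015 | 83 | 107 |
| 28 Mar 2015 | 24 Mar 2015 | day | 10 Mar 2015 | 0 | 18 |
| 20 Nov 2015 | 5 Nov 2015 | month and day | 10 Mar 2015 | 0 | 255 |
| 20 Feb 2016 | 5 Feb 2016 | month and day | 1 Jan 2016 | 297 | 347 |

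In every row the imputed death precedes the last date seen alive; in the first row by 15 days. The last row shows that a year-only death in a later calendar year is dated too early but not at zero.

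**Size of the shift, day missing.** The shift is (day of month − 1). Over a 365-day year, before the day-one limit: (7 × 465 + 4 × 435 + 378) / 365 = 5373 / 365 = 14.7 days, maximum 30.

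**Chance that the imputed date precedes last contact, day missing.** This is the share of calendar dates whose day of month exceeds the gap plus 1.

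| Last contact before death (assumed) | Chance |
|---|---|
| 3 days | 87% |
| 7 days | 74% |
| 14 days | 51% |
| 21 days | 28% |
| 28 days | 5% |

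**Chance of OS = 0, only the year known.** With first doses spread evenly over the year (assumed) and true survival T below 365 days, the chance is (365 − T) / 365.

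| T (days) | Chance of zero |
|---|---|
| 60 | 84% |
| 120 | 67% |
| 183 | 50% |
| 270 | 26% |
| 330 | 10% |
| 365 | 0% |

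For scale, Protocol section 3.1 expects participation of about 6 months. That is time on study, not survival.

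**Effect on the Kaplan-Meier curve.** With 20 expansion patients, one death is a step of 1/20 = 5 points. The patient is counted as a death under any rule. If no one is censored between the imputed and true dates, the curve is 5 points too low over that interval and correct afterwards. If the true death came before the median, the median does not change; if after, it moves by about one order statistic.

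**Side effect on PFS.** SAP section 7.1 counts a death within 28 days of discontinuation as an event. A death 35 days after discontinuation with the day missing is pulled inside that window in 77% of calendar positions; at 45 days, 44%.

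**The case against.** The strongest reply is that this is an edge case in a descriptive analysis. SAP sections 4.1 and 9.1 plan no hypothesis test, and Protocol section 9.4 presents PFS and OS only if the data permit. The rule is also said to follow a sponsor standard that is not part of the documents and might contain a floor. The low consequence stands. The appeal to an unseen standard helps less, because the SAP spells out its own limit, and a programmer following that text would produce the results above.

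A reader might infer more than the documents support:
- **Progression dates are backdated too.** Section 8.1 would technically reach them, but Appendix 3 takes progression from the tumor assessment that shows it. Nothing suggests that scan dates will be partial.
- **PFS can collapse to zero.** It cannot: the formula adds 1, so the minimum is 1 day. Deaths counted for PFS also fall largely in the period of active SAE reporting and the 28 to 35 day follow-up contact, where partial dates are least likely.
- **A false time-zero death costs 5 points of survival.** It brings forward a step that the curve takes anyway.
- **Late deaths are the ones most likely to be partly dated.** No passage supports this. Scheduled follow-up ends at 28 to 35 days unless toxicity continues, so a late death may simply not be captured. That is a separate matter.

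**Conclusion.** The concern holds for death dates, and its practical weight is small. As written, the rule can place a death before a date on which the patient is documented alive, and it gives an OS of 0 days for a year-only death in the year of first dose. A missing day gives 0 as well if death falls in the month of first dose. These results follow from the stated rule and do not depend on any detail that the plan leaves open.

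The mean backward shift for a missing day is about 15 days, with a maximum of 30. The percentages rest on assumed contact gaps, survival times and evenly spread calendar dates. How many death dates will be partial is unknown and may be none. The effect falls mainly on the timing of deaths in the OS estimate for about 20 patients. DLT, MTD and response rate do not depend on it.

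**What to change.** Add a provision to SAP section 8.1 for death dates only: impute as now, but no earlier than the day after the last date the patient is documented alive, and no later than the end of the known month or year. The upper limit is needed when, for example, the patient was seen on the last day of the month in which death occurred.

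In the four worked cases the floor gives 99, 15, 241 and 333 days, against 83, 0, 0 and 297 under the present rule and true values of 107, 18, 255 and 347. The imputed times remain somewhat short but no longer contradict the record.

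Leave the rule for adverse event onset unchanged. State that progression dates come from the dated tumor assessment. Do not apply the floor to last-contact dates: last contact is itself the last date documented alive, so the floor would be circular and could credit an undocumented day.

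The cost is one or two SAP sentences and a derived variable for last date alive, built from visit, laboratory and telephone-contact dates. No procedure or data collection changes.
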